Study objectives:	
 1. Comparative assessment of efficacy of Primapur[®] (follitropin alfa), a solution for subcutaneous administration, and GONAL-F[®] (follitropin alfa). 2. Comparative assessment of safety of Primapur[®] (follitropin alfa), a solution for subcutaneous administration, and GONAL-F[®] (follitropin alfa).
Study design:	
multicenter randomized embryologically blinded parallel group comparative therapeutic equivalence study of Primapur[®], a solution for subcutaneous administration, and GONAL-f[®], a solution for subcutaneous administration.

Planned number of patients	
110 female patients randomized into two equal groups of 55 subjects receiving study referenced drugs.

Study centers	
3 specialized medical centers in the Russian Federation

Study population:	
Women aged 20-35 with established causes of infertility (tubal factor, male factor (oligoasthenoteratozoospermia) and indications for the use of assist reproductive technologies (ART).

Inclusion criteria:	
 1. Women with established causes of infertility and indications for the use of ART methods, according to the Order of the Ministry of Health of the Russian Federation "On the use of assisted reproductive technologies, contraindications and limitations to their use" No. 107 n dated August 30, 2012. 2. Causes of infertility: Tubal factor and/or male factor (oligoasthenoteratozoospermia). 3. Female patients aged 20 to ≤35 with an independent regular menstrual cycle (duration: 21 to 35 days); 4. First or second attempt of IVF/ICSI.

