
Statistical processing of data:
	
Description of methods of statistical data processing
 
The quantitative data obtained during the study will be tested for normal distribution, using the Shapiro-Wilk test and, if necessary, the F-test of equality of variances. For variables corresponding to the normal distribution, mean values and standard deviation of the mean will be calculated; Quantitative data not corresponding to the normal distribution will be described using the median and interquartile interval. Qualitative variables will be described using absolute and relative frequencies (percentages).
 
In order to compare two groups of normally distributed quantitative data, the Student's t-test will be used; if quantitative data distribution differs from normal values, the Mann-Whitney U test will be used. For intergroup comparisons by qualitative characteristics, the Fisher's exact test will be used; correction of p-value in the case of multiple hypotheses will be realized through the Bonferroni adjustment.
 
Applicable significance level
 
In this study, the indicators are considered statistically significant at the bilateral p-value level <0.05.
 
Therapeutic equivalence criteria.
 
The conclusion about the therapeutic equivalence of the two drugs will be made if the difference between the mean values of the total number of oocytes obtained when applying both drugs lies within the limits of the equivalence threshold (± 3.4 oocytes).
 
Procedures for accounting of missing, not-analyzable and uncertain data.
 
CRF information will be entered into the computer database, and data will be electronically and visually verified for completeness, and allowable ranges will be checked. All errors detected during the quality control process will be corrected. In the presence of deviating data ("outliers"), the correctness of their measurement and introduction into the database will be rechecked. Data will be analyzed twice: with and without "outliers". If the results are stable to the "outliers", a calculation that includes all available values of the variable will be used. If there is the influence of "outliers" on the initial result, the results obtained both taking into account the deviating data and without deviating data will be presented and commented on.

Calculation of sample size

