For the present study, calculation of sample size is based on data on the number of oocytes obtained from clinical studies of GONAL-F® (follitropin alfa) and its biosimilars (*Rettenbacher M. et al. Reprod Biomed Online. 2015;30(5):504-13; Strowitzki T. et al. Reprod Biol Endocrinol. 2016;14:1.; Moon SY et al. J Obstet Gynaecol Res. 2007;33(3):305-15*).

Based on the results of these studies, it is assumed that the total number of oocytes obtained for study and reference product of follitropin alfa is 12.0 ± 5.9 and 10.9 ± 6.5 , respectively.

To suppress the release of endogenous LH, ART programs use either GnRH antagonist or GnRH agonist, together with the use of follitropin. According to meta-analyzes (*van Wely M. et al. Cochrane Database Syst Rev. 2011;(2):CD005354; Al-Inany HG et al. Cochrane Database Syst Rev. 2016; 4: CD001750*), the use of GnRH agonists and antagonists in ART programs leads to the same number of live births; and the use of GnRH antagonist statistically significantly reduces the risk of serious adverse events, compared with the use of GnRH agonist; however, the number of oocytes obtained may differ slightly in the protocols with the use of GnRH antagonists, which is explained by the difference in growth of a size-synchronized pool of follicles.

In accordance with this, the following hypotheses have been formulated:

H0 (zero hypothesis): $\mu_A - \mu_B \leq -d, \mu_A - \mu_B \geq +d$

H1 (alternative hypothesis): $-d < \mu_A - \mu_B < +d$

where μ_A and μ_B are the selective average number of oocytes of study drug and reference drug (GONAL-F®).

The required number of patients in equal parallel groups was calculated according to the following formula (*Julious, SA. Statist. Med. 2004; 23:1921-1986*):

$$1 - \beta = \text{Probt}(-t_{1-\alpha, n_A(r+1)-2, n_A(r+1)-2, \tau_2}) - \text{Probt}(t_{1-\alpha, n_A(r+1)-2, n_A(r+1)-2, \tau_1})$$

where τ_1 and τ_2 are the uncertainty parameters calculated by the following formulas:

$$\tau_1 = \frac{((\mu_A - \mu_B) + d)\sqrt{rn_A}}{\sqrt{(r+1)\sigma^2}} \quad \tau_2 = \frac{((\mu_A - \mu_B) - d)\sqrt{rn_A}}{\sqrt{(r+1)\sigma^2}}$$

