Thus, to provide a study power of at least 80% at a significance level $\alpha=0.05$, a standard deviation of the number of oocytes obtained equal to $\sigma=6$ and an equivalence threshold value $d = 3.4$ oocytes, the required sample size is 55 subjects per each group (n_A) and only 110 subjects in total; taking into account 27% drop out, the number of screened patients is recommended to be increased to 140.

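### The stated power of at least 80% with 55 per group requires a true difference of essentially zero, which the plan never states; at its own assumed means power is about 60–63%

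*Combined protocol and SAP*

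**What the plan says.** Under *Calculation of sample size* in the study summary, the plan draws on earlier trials of the reference product and its biosimilars. On that basis it takes as its assumption that the "total number of oocytes obtained for study and reference product of follitropin alfa is 12.0 ± 5.9 and 10.9 ± 6.5", respectively. The equivalence hypotheses follow, with a non-central t power formula in which μA − μB enters both non-centrality terms, τ1 and τ2.

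The conclusion is that, "to provide a study power of at least 80% at a significance level" of 0.05, with σ = 6 and d = 3.4, "the required sample size is 55 subjects per each group". No value of μA − μB appears among these inputs. After a 27% drop-out allowance, "the number of screened patients is recommended to be increased to 140".

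Two other entries bear on the point. *Planned number of patients* gives "110 female patients randomized into two equal groups of 55 subjects". *Applicable significance level* says that "the indicators are considered statistically significant at the bilateral p-value level <0.05".

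**The concern.** The power of an equivalence test depends strongly on the true difference, because any real difference uses up part of the margin. The only means in the plan differ by 1.1 oocytes, about a third of the 3.4 margin (1.1 / 3.4 = 0.32). The sample size statement is presented as following from those means, but the difference is missing from its inputs. Nothing in the documents says that zero was used instead, or why 1.1 was set aside.

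The power statement is the only justification given for the number of patients. If it holds only for a difference that the plan does not assume, readers are misled about how likely the trial is to answer its question.

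**Working it through.** **Inputs** (all from *Calculation of sample size* unless noted)

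- Margin d = 3.4; σ = 6; n = 55 per group; allocation ratio r = 1.
- α = 0.05, entering the formula as t(1−α), so 0.05 for each one-sided test.
- Assumed means 12.0 and 10.9, so μA − μB = 1.1. Stated SDs 5.9 and 6.5.
- Equal-weight pooled SD = √((5.9² + 6.5²)/2) = √38.53 = 6.21. Equal weighting is my assumption, because the source group sizes are not given.

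**Formula** (the plan's own, with r = 1)

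Power = Probt(−t; 2n−2, τ2) − Probt(t; 2n−2, τ1), where t = t(1−α, 2n−2), τ1 = (Δ + d)/SE, τ2 = (Δ − d)/SE, SE = σ√(2/n) and Δ = μA − μB.

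**Step 1: reproduce the plan's 55.** Take Δ = 0 and σ = 6.

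- n = 54: power 79.97%.
- n = 55: SE = 6 × √(2/55) = 1.144; t = 1.659 on 108 df; τ1 = 3.4/1.144 = 2.97; τ2 = −2.97. Power = 0.9046 − 0.0954 = 0.809.

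So 55 is the smallest n that reaches 80% at zero difference. The plan's figure is reproduced, but only with that unstated input.

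**Step 2: use the plan's assumed difference.** Take Δ = 1.1, n = 55 and σ = 6.

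τ1 = 4.5/1.144 = 3.93; τ2 = −2.3/1.144 = −2.01. Power = 0.6379 − 0.0118 = 0.626.

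**Step 3: vary the difference and the SD at n = 55.**

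| Δ | SD | Power |
|---|---|---|
| 0 | 6 | 80.9% |
| 0.23 | 6 | 80.0% |
| 0.25 | 6 | 79.9% |
| 0.5 | 6 | 76.8% |
| 1.1 | 6 | 62.6% |
| 1.1 | 5.9 | 64.1% |
| 1.1 | 6.21 | 59.6% |
| 1.1 | 6.5 | 55.4% |
| 0 | 6.21 | 77.4% |

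With SD 6, power crosses 80% at Δ = 0.234. With SD 6.21 it is below 80% even at zero difference. Numerical integration of the exact two one-sided test power agrees with the formula to four decimals.

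**Step 4: could something else explain the gap?**

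- *A different SD.* Power of 80% at Δ = 1.1 with n = 55 needs an SD of about 4.8, below both stated SDs.
- *The 140 patients.* That is a number to screen; 110 are to be randomized. Even 70 analysed per group (140/2) would give 72.7% (SD 6) or 70.0% (SD 6.21) at Δ = 1.1.
- *A different α.* Reading the two-sided 0.05 as 0.025 per side gives 67.5% at Δ = 0 and 48.7% at Δ = 1.1 (SD 6). This widens the gap and does not reproduce 55.

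For scale, the formula first reaches 80% at Δ = 1.1 with 85 per group (SD 6) or 91 (SD 6.21).

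**The case against.** The strongest reply is that nothing was miscalculated. The formula gives 55 at zero difference, and zero is an understandable planning value for a study meant to confirm biosimilarity. On this reading the quoted means are background for choosing an SD, and 1.1 is never called the planning difference. It is true that the arithmetic is sound at zero, and planning at zero can be defended. But the plan does not say that it did so. It presents 12.0 and 10.9 as its assumption for the two products, follows them with a formula that needs their difference, and does not limit their use to the SD. They do not yield σ = 6 by simple pooling either.

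A second reply is that a 37–40% chance of failure presupposes an interval-based decision. *Therapeutic equivalence criteria* mentions only the difference in means lying within ±3.4. If only the point estimate had to lie inside the margin, a normal calculation puts failure at Δ = 1.1 at about 2% (SD 6: 2.3/1.144 = 2.01 standard errors) to 3% (SD 6.21). The condition is a fair one, and the 37–40% should be quoted with it. It does not rescue the power claim, which comes from the two one-sided test formula and has to be judged by it.

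A third reply is that correcting the text leaves the trial's actual power unchanged. That is so, but the claim as written is still not supported by the plan's own assumptions.

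**Conclusion.** The concern holds. The power of at least 80% is correct only for a true difference between zero and about 0.23 oocytes at SD 6, and the plan neither states nor justifies that input. At its own assumed difference of 1.1, power with 55 per group is 62.6% (SD 6) or 59.6% (SD 6.21). Across the two stated SDs taken singly, the range is 55.4% to 64.1%. The implied chance of not showing equivalence is about 37–40% (100 − 62.6 = 37.4; 100 − 59.6 = 40.4), roughly double the 20% that the plan implies.

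These figures rest on two one-sided tests at 0.05 each, as in the plan's formula, on 55 analysed patients per group, and, for SD 6.21, on equal weighting. The chance of wrongly declaring equivalence is not raised. What is wrong is the stated likelihood of a conclusive result, and it should be corrected.

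**What to change.** In the closing paragraph of *Calculation of sample size*, state the value of μA − μB that was used and, if it was zero, why the 1.1 was set aside. Replace the power statement with wording such as:

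> With two one-sided tests at 0.05 each, an equivalence margin of ±3.4 oocytes and 55 analysed patients per group, power is 81% if the true difference is zero and the SD is 6. If the true difference is the 1.1 oocytes assumed above, power is about 63% with an SD of 6.0 and about 60% with an SD of 6.2 (equal-weight pooling of the two SDs given above).

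Say also how σ = 6 was obtained. The wording adopts the formula's 0.05 per side, so the plan should make clear that its general two-sided 0.05 level does not govern the equivalence test.

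This is a text change. Enrolment, margin, endpoint and conduct stay as they are. The cost is a less favourable stated power.

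### The sample size uses an SD of 6, but the plan's own planning SDs pool to 6.21; at that value 55 per group gives about 77% power at best, not at least 80%

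*Combined protocol and SAP*

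**What the plan says.** All the relevant text is in the combined protocol and SAP, in the study summary under Statistical processing of data, subsection Calculation of sample size.

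- **Planning values.** Citing published studies of the reference product and its biosimilars, the plan assumes that the oocyte count for the study and reference "product of follitropin alfa is 12.0 ± 5.9 and 10.9 ± 6.5", respectively.
- **Formula.** It uses a noncentral-t power formula for equivalence of two parallel groups. The formula has one common σ, an allocation ratio r, a margin d, a true difference μA − μB and a critical value at 1 − α.
- **Inputs and result.** The calculation is meant "to provide a study power of at least 80"%, with α = 0.05, "a standard deviation of the number of oocytes obtained equal to" 6 and d = 3.4 oocytes. The result is 55 per group, 110 in total. The row on the planned number of patients confirms two equal groups of 55.

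The section does not explain how 5.9 and 6.5 become 6, names no other source for 6, and does not state the value of μA − μB that was entered.

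**The concern.** The SD is one of the two inputs, with the assumed true difference, that decide whether 55 per group is enough. The plan offers 5.9 and 6.5 as the basis of its calculation, then uses a value well below their midpoint. The change is in the favourable direction and it matters because 55 has almost no slack: at an SD of 6, 54 per group already falls just short of 80%. A small increase in the SD therefore takes the design below its stated floor.

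At stake is the power statement for the primary endpoint of an equivalence trial. The margin, the type I error and the equivalence criterion are not affected.

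**Working it through.** **Inputs, all from the subsection Calculation of sample size unless noted.** SDs 5.9 (study) and 6.5 (reference); means 12.0 and 10.9; σ = 6; d = 3.4; α = 0.05, entering the formula as the 1 − α quantile, so two one-sided tests at 0.05 each; r = 1 (equal groups, also in the planned number of patients).

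**Formula with r = 1.** SE = σ√(2/n), df = 2n − 2, τ1 = ((μA − μB) + d)/SE, τ2 = ((μA − μB) − d)/SE.
Power = P(T ≤ −t; df, τ2) − P(T ≤ t; df, τ1), where T is noncentral t and t is the 0.95 quantile of central t.

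**Step 1: reproduce the plan's figure.** For σ = 6, n = 55 and zero difference:
- SE = 6 × √(2/55) = 1.144; τ1 = 3.4/1.144 = 2.97 and τ2 = −2.97; df = 108, t = 1.659.
- Power = 80.9%. At n = 54 it is 79.97%, so 55 is the smallest n reaching 80%.

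The unstated inputs can be inferred from this. A true difference of 1.1 would need 85 per group, and one-sided tests at 0.025 would need 67. Of these readings, only zero difference with one-sided 0.05 gives 55.

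**Step 2: the SD implied by the planning values.** The variance of the difference in means with n per arm is 5.9²/n + 6.5²/n = (34.81 + 42.25)/n = 77.06/n. Setting this equal to 2σ²/n gives σ² = 38.53 and σ = 6.207. The sizes of the cited studies do not enter, because the 1:1 allocation of this trial sets the weights. To average the variances to 36, the reference arm would need a weight of (36 − 34.81)/(42.25 − 34.81) = 1.19/7.44 = 16%, which does not fit equal arms.

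**Step 3: rerun with that SD.** For σ = 6.207, n = 55 and zero difference: SE = 1.184, τ1 = 2.87, τ2 = −2.87, power = 77.4%. The smallest n for 80% is 58 per group. The largest σ at which 55 per group still gives 80% is about 6.05.

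**Step 4: the difference implied by the same sentence.** 12.0 − 10.9 = 1.1 oocytes.

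| σ | Power at 55 per group, difference 0 | n per group for 80% | Power at 55 per group, difference 1.1 | n per group for 80% |
|---|---|---|---|---|
| 6.0 (plan) | 80.9% | 55 | 62.6% | 85 |
| 6.207 (from 5.9 and 6.5) | 77.4% | 58 | 59.6% | 91 |
| 6.5 in both arms (sensitivity only) | 72.0% | 64 | 55.4% | 100 |

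**The case against.** The case for leaving the text alone has real force.

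- **The calculation is correct as stated.** The power claim is conditional on σ = 6, and with that input 55 per group reproduces exactly. This stands. A reader might infer a computing error from the gap between 77% and 80%, but the documents do not support that. The fault is an input that does not match its stated basis.
- **Rounding a planning SD is ordinary judgement.** The change is about 0.2 oocytes, 6 lies between 5.9 and 6.5, and the true SD is unknown. This is why the point is modest. It does not remove it: the plan promises a floor, n was set at the bare minimum, and the rounding crosses the 80% line without explanation.
- **Taking the SDs from that sentence but not the means is selective.** This is the strongest objection, and it stands against quoting 77% alone. If the sentence governs, its 1.1-oocyte difference governs too, and power is about 60%. The 77% is therefore a best case and should be reported next to the 60%.
- **An SD of 6.5 is not a plan value for both arms.** Correct: the study product is given 5.9. A reader might conclude that the design has only 72% power or needs 64 per group. The documents do not support that, and these figures serve only as a sensitivity check.

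**Conclusion.** The point holds as a mismatch between the SD entered and the SDs on which the plan says it relies. With the plan's own SDs, 55 per group gives about 77% power at zero true difference. That is 2.6 percentage points below the stated floor, equivalent to three patients per group (58 against 55).

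The result assumes the plan's own formula, two one-sided tests at 0.05, a margin of 3.4, all 55 per arm analysed, and a true difference of exactly zero, the most favourable case. The assumed difference has the larger effect: at 1.1 oocytes power is about 63% with σ = 6 and about 60% with σ = 6.21.

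A reader might go further and conclude that the trial is bound to be underpowered or must be enlarged. The documents do not establish that, since the actual SD and the actual difference are unknown. They show only that the stated power does not follow from the stated assumptions.

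**What to change.** In the closing paragraph of the subsection Calculation of sample size:

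1. Use σ = 6.2. Alternatively, state where 6 comes from and reconcile it with 5.9 and 6.5. Keep those SDs in the text either way, because they are the only variability data that the plan reports.
2. State the true difference assumed in the calculation.
3. Restate the power of 55 per group as about 77% at zero difference and about 60% at the 1.1-oocyte difference implied by the planning means.
4. If a range is wanted, show an SD of 6.5 in both arms (72% at zero difference) as a sensitivity value and label it as such.

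The cost is a sentence or two and a less favourable power statement. No extra patients are requested, and no procedure, margin or analysis changes.

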
Exclusion criteria:
	
 1. The patient's refusal to participate in the study at any stage. 2. Development of one of the exclusion criteria. 3. Development of severe OHS. 4. Ineffective stimulation of FSH (no pool of growing follicles) on Day 5 or Day 8 of stimulation. 5. Necessity of cryopreservation of embryos due to cancellation/postponement of embryo transfer according to the indications. 6. Development of AEs/adverse reactions that cause an unacceptable risk to the patient's health if the patient continues to participate in the study

	
and requires the withdrawal of the therapy and/or the concomitant therapy.
 
7. The patient's major violation of the medical investigator's recommendations under the protocol and deviation from the study procedures.
 
8. Occurrence of concomitant somatic diseases/symptoms or aggravation of chronic diseases not associated with taking medications (at the discretion of the medical investigator), requiring changes in therapy and observation procedures that are incompatible with the clinical study protocol.

Dosage and duration of treatment; route of administration:
	
QD, starting from Day 2 of Day 3 of menstrual cycle, 150 IU of study/reference drug per day, according to the protocol controlled superovulation induction, with the use of GnRH antagonist, providing the ability to adjust the dose of study drug on Day 5 or Day 8 of stimulation as a result of transvaginal ultrasound of ovaries. The duration of stimulation is no more than 15 days.

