
Screening period. 4 weeks.
	
Visit 1. Screening (Day -28 to Day 1). At this visit, the use of the results of routine studies and analysis is permissible, if the term of their implementation is within the 4-week screening period and the conclusion/outcome includes the listed parameters. Exceptions are laboratory clinical blood and urine tests (complete blood count, biochemical blood test, common urine analysis) which must be performed in one laboratory at all stages of the clinical study. All screening procedures should be performed prior to randomization of the patient.
 
 1. The patient's informed consent. 2. Initial observation by obstetrician-gynecologist (reproductologist): 
 ✓ History taking (medical history, life history, gynecological history, family history), registration of concurrent conditions and concomitant therapy. ✓ Gynecological examination. ✓ Physical examination ✓ Measurement of vital parameters, particularly HR, BP, RR, body temperature. ✓ Registration of patient complaints. 3. Instrumental examinations: 
 ✓ Ultrasound of the pelvic organs, including transvaginal ultrasound of the uterus and ovaries; assessment of the state of the endometrium and the presence/absence of signs of pregnancy; ✓ Transvaginal ultrasound of ovaries for the absence of cysts and endometrial pathology (performed strictly according to the schedule on Day 1, before the procedure of randomization of the patient).

	
 4. Laboratory testing: 
 ✓ Complete blood count. ✓ Biochemical blood test. ✓ Blood sampling for the analysis of anti-FSH antibodies* (point "0"). ✓ General urine analysis. ✓ Blood hormones: AMH; on Day 2-5 of the menstrual cycle: FSH, LH, estradiol, prolactin, bound testosterone, cortisol, TSH, ACTH, STH. ✓ Coagulogram. ✓ Smear on the flora. 5. Husband (partner) inspection: 
 ✓ Laboratory tests - spermogram.

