
Period of PI/PR therapy. Up to 15 days (2 weeks and 1 day).
	
Visit 2. Randomization. Day 1. Beginning of the stimulation protocol (2-3 day of the menstrual cycle)
 
 1. Selection criteria check. Decision of randomization into a clinical study or registration of a screening failure. 2. Carrying out randomization, using IWRS, distribution into groups: group FSG031 of Primap[®], a study drug, or group FSG032 of GONAL-f[®], a reference drug. 3. Inspection: 
 ✓ Registration of patient complaints. ✓ Registration of changes in concurrent conditions and concomitant therapy. ✓ Physical examination ✓ Measurement of vital parameters, particularly HR, BP, RR, body temperature. ✓ Prescription of the stimulation protocol. 4. Introduction of the 1st dose of PI/PR. 5. Registration of adverse events/reactions after the first dose of PI/PR. 
Visit 3. Day 5-8 of stimulation.
 
The 3rd visit procedures are aimed at a primary evaluation of the therapy efficacy. The patient may be invited to conduct the procedure once (on the 5th day) or several times (additionally on the 6th, 7th, 8th days of the therapy) at the investigator's discretion, depending on the results of the required diagnostic procedures. 3 visit procedures:
 
 1. Instrumental examinations: 
 ✓ Transvaginal ultrasound of ovaries. Follicle count and determination of follicle diameter in both ovaries. 2. Inspection: 
 ✓ PI/PR dose adjustment (in the absence of follicles more than 10 mm on 5-8 days of stimulation).

- ✓ Registration of patient complaints, concurrent conditions and concomitant therapy.
 - ✓ Physical examination
 - ✓ Measurement of vital parameters, particularly HR, BP, RR, body temperature.
3. *Exclusion of the patient from the study in case of failed stimulation (with no response to FSH administration on day 5-8 of stimulation).*
 4. Initiation of GnRH antagonist administration (when the lead follicle is about 14 mm);
 5. Registration of adverse events/reactions.

Additional visit for GnRH antagonist administration (if required).

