Unscheduled visit.	
At any stage of the study, an additional visit to the center can be made at the investigator's discretion if a patient has a complaint requiring a reproductologist's intervention for the purpose of individually monitoring the superovulation induction course and monitoring the pregnancy course in order to reduce the risk of developing any adverse reaction and to monitor the therapy efficacy.
 
Additional visits may include, but not be limited to, the following procedures (depending on the indications):
 
 1. Instrumental examinations: 
 ✓ Transvaginal ultrasound of ovaries. 2. FSH dose adjustment. 3. Physical examination. 4. Measurement of vital parameters. 5. Registration of patient complaints. 6. Complete blood count. 7. Biochemical blood test. 8. Coagulogram. 9. General urine analysis.

	10. Blood test for hormones and other clinically relevant markers.

*The presence of anti-FSH antibodies will be determined centrally at the laboratory of Exacte Labs LLC and/or an additional research laboratory on a contractual basis (if required). The study results will be attached to the initial documentation of the investigation site. Immunogenicity will be evaluated using the following methods: enzyme immunoassay and surface plasmon resonance for positive samples.
	

Efficacy evaluation criteria:
	
Study endpoints per patient:
 
Primary point:
 
 • Total number of aspirated oocytes. 
Secondary points:
 
 • Number of follicles \geq 16 mm on the day of administration of hCG. • Number of mature oocytes (MII stage). • Number of fertilized oocytes. • Number of patients with embryo transfer (days 2-3). • Number of patients with blastocyst transfer (days 4-5). • Total dose of a human rFSH product injected (IU). • Number of days of stimulation. • Percentage of patients who needed a FSH dose adjustment on the 5th-8th day of stimulation. • Number of patients who abandoned the IVF/ICSI program in the process of stimulation. • Number of non-responders to stimulation. • Incidence of biochemical pregnancies. • Incidence of clinical pregnancies (up to 10 weeks after the embryo(s) transfer).

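### The 27% drop-out and 140 screened do not agree (27% needs 151), and 110 randomised gives at least 80% power only if the true difference is near zero and almost no oocyte counts are missing

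*Combined protocol and SAP*

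**What the plan says.** The document is the combined protocol and SAP.

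- **Calculation of sample size, conclusion.** With α = 0.05, SD 6 and margin 3.4 oocytes, 55 patients per group (110 in total) are required for at least 80% power. The text continues: "taking into account 27% drop out, the number of screened patients is recommended to be increased to 140". No true difference is given beside the 80%.
- **Calculation of sample size, assumed means.** The expected number of oocytes for "study and reference product of follitropin alfa is 12.0 ± 5.9 and 10.9 ± 6.5", respectively, which is a difference of 1.1.
- **Planned number of patients.** "110 female patients randomized into two equal groups of 55 subjects".
- **Visit 1, Screening.** "All screening procedures should be performed prior to randomization of the patient".
- **Exclusion criteria, second list (withdrawal during the study), item 4.** "Ineffective stimulation of FSH (no pool of growing follicles) on Day 5 or Day 8 of stimulation". Visit 3, item 3, repeats this: "Exclusion of the patient from the study in case of failed stimulation". Both come before the oocyte count at Visit 5.
- **Efficacy evaluation criteria, secondary points.** These include "Number of patients who abandoned the IVF/ICSI program in the process of stimulation".
- **Statistical processing of data.** The paragraph headed "Procedures for accounting of missing, not-analyzable and uncertain data" deals with database checks and outliers. It has no rule for a patient who has no aspiration.

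**The concern.** There are two separate problems.

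First, the 27% and the 140 do not belong together. The figure 140 comes from multiplying by 1.27, whereas allowing for a loss of 27% means dividing by 0.73.

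Second, the sentence reads as if drop-out had been provided for, but the allowance is attached to patients screened. Screening is complete before randomisation, so it cannot replace anyone lost afterwards. The number randomised equals the number the formula needs with an oocyte count, while the plan itself foresees withdrawals between randomisation and the count. The power formula also contains the true difference μA − μB, so the 80% has no definite meaning until that value is named, and the section's own assumed means do not give zero.

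At stake is whether the stated power, on which the size of this equivalence trial rests, is the power the trial would have.

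**Working it through.** **Inputs.** From the sample-size section: SD σ = 6, margin d = 3.4, α = 0.05 in each of two one-sided tests (the formula uses t at 1 − α), equal groups (r = 1), assumed means 12.0 and 10.9. From the planned number of patients: 55 + 55 randomised. The documents give no rate of loss after randomisation, so the rates below are assumptions.

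**Step 1. The screening number.**

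- 110 × 1.27 = 139.7, so 140. This reproduces the plan's figure.
- A 27% loss: 110/(1 − 0.27) = 110/0.73 = 150.7, so 151.
- Loss implied by 140 → 110: 30/140 = 21.4%.
- 140 with a 27% loss: 140 × 0.73 = 102.2, so 102.
- 30/110 = 27.3%. The pair fits only if 27% means the excess screened over the number randomised.

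**Step 2. Reproducing 55 per group.** With n per group,

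SE = σ√(2/n), τ1 = ((μA − μB) + d)/SE, τ2 = ((μA − μB) − d)/SE,

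power = Probt(−t, 2n − 2, τ2) − Probt(t, 2n − 2, τ1), where t is the 0.95 quantile on 2n − 2 degrees of freedom.

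At n = 55: SE = 6 × √(2/55) = 1.144 and t = 1.659.

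- True difference 0: τ1 = 3.4/1.144 = 2.97, τ2 = −2.97, power 80.9%. At n = 54 it is 79.97%, so 55 is the exact minimum.
- The largest true difference that keeps 80% at 55 per group is about 0.23 (80.03% at 0.23, 79.96% at 0.24).
- True difference 12.0 − 10.9 = 1.1: τ1 = 4.5/1.144 = 3.93, τ2 = −2.3/1.144 = −2.01, power 62.6%. Reaching 80% would take 85 per group.

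The plan's 55 is therefore reproduced only for a true difference between 0 and about 0.23.

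**Step 3. Patients without an aspiration treated as missing.** For unequal groups, SE = σ√(1/n1 + 1/n2). Exact integration confirms the formula's results.

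| With a count | Loss | Power, difference 0 | Power, difference 1.1 |
|---|---|---|---|
| 55/55 | none | 80.9% | 62.6% |
| 55/54 | one patient | 80.4% | – |
| 54/54 | two patients | 79.97% | – |
| 52/52 | 5% (assumed; 104.5 of 110) | 78.0% | 60.1% |
| 50/49 | 10% (assumed; 99 of 110) | 75.2% | 57.9% |
| 44/44 | 20% (assumed; 88 of 110) | 67.9% | – |

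**Step 4. Patients without an aspiration counted as zero.** The groups stay at 55/55 but the SD rises. Assume a share p of zeros in both groups, and mean 11.45 (midpoint of 12.0 and 10.9) with SD 6 among the others:

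variance = (1 − p)(36 + 11.45²) − ((1 − p) × 11.45)².

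- p = 5%: variance 40.43, SD 6.36, power 74.6% at difference 0.
- p = 10%: variance 44.20, SD 6.65, power 69.2% at difference 0.

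A simulation of 100,000 trials gave 74.5% and 69.1%. If the SD of 6 already includes zeros, power stays at 80.9%.

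**The case against.** The figures are not in dispute; the objection is to their weight.

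The plan ties the 27% to screening, only recommends 140, and fixes 110 randomised. The natural reading is a loosely worded screening allowance, and no passage says that screening stops at 140. That stands: the first problem alone has no effect on inference.

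Losses before the count may also be few. Eligibility sets limits on AMH, antral follicle count and basal FSH, and excludes previous poor responders. Withdrawal for cryopreservation is listed after the oocyte count, so it need not cost a primary endpoint value. Two missing counts lower power to 79.97%, which is hardly a failure. The larger falls need loss rates that the documents do not give, and the zero-count figures depend on what the SD of 6 represents. All of this stands, and those figures are illustrations only.

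Finally, planning an equivalence trial at a true difference of zero is a usual choice, and that question is distinct from drop-out. Zero may well have been intended. But the section does not say so, and the only expected means it gives differ by 1.1. The 62.6% needs no assumed loss, so this part of the concern is unaffected.

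**Conclusion.** The concern holds. A 27% loss needs 151 screened, not 140; equivalently, 140 allows for a loss of 21.4%. This is a minor error that touches only the screening target, provided 110 are randomised.

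The claim of at least 80% power is not supported as written. With SD 6, margin 3.4 and one-sided 0.05 tests, it is true only for a true difference up to about 0.23 with all 110 counts present or, at a difference of exactly 0, with at most one count missing. A few losses cost little (78.0% at an assumed 5%). The main shortfall comes from the unstated true difference: at the section's own 1.1, power is 62.6% before any loss. The missing-count results assume that patients without an aspiration drop out of the primary analysis, which the plan neither says nor rules out.

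**What to change.** 1. **Screening sentence.** Change 140 to 151, or change 27% to 21%, or say that 27% more patients are screened than randomised. State that the allowance is for screening failure, if that is what is meant.
2. **Patients without an aspiration.** State, before data are seen, whether they enter the primary analysis as zero oocytes or as missing.
3. **Power statement.** Keep 110 randomised. Replace the claim of at least 80% with the power at the expected number per group with a count, over a stated range of loss rates, and name the assumed true difference beside it. If such patients are missing, for example: true difference 0, 80.9% with no losses, 78.0% at 5%, 75.2% at 10%; true difference 1.1, 62.6%, 60.1% and 57.9%.

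The cost is a text correction. No more patients are randomised, and about 11 more are screened (151 − 140) only if 151 is adopted. The stated power becomes less favourable.
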